8.5.2 Secondary analyses

Secondary analyses will be performed for the patient populations defined earlier, and according to the overview below.

Patient Population	Secondary Objectives	Outcome Measures

 • HRR_m • All 	To assess the efficacy of the combination of ceralasertib +olaparib and the combination of AZD1775+olaparib compared with olaparib monotherapy by assessment of PFS	PFS using Blinded Independent Central Review (BICR) according to Response Evaluation Criteria in Solid Tumours (RECIST 1.1) Sensitivity analysis of PFS using Investigator assessments according to RECIST 1.1

Patient Population	Secondary Objectives	Outcome Measures

 • BRCAm • HRRm • Non BRCAm HRRm • All • Non HRRm 	
To assess the efficacy of the combination of ceralasertib +olaparib and the combination of AZD1775+olaparib compared with olaparib monotherapy in terms of
 
 • ORR 	
Objective response using BICR according to RECIST 1.1 Sensitivity analysis of objective response using Investigator assessments according to RECIST 1.1

 • BRCAm • Non BRCAm HRRm • Non HRRm 	
To assess the efficacy of the combination of ceralasertib +olaparib and the combination of AZD1775+olaparib compared with olaparib monotherapy in terms of
 
 • DoR • tumour change 	
DoR and tumour change using BICR according to RECIST 1.1 Sensitivity analysis of DoR, and tumour change using Investigator assessments according to RECIST 1.1

 • BRCAm • HRRm • Non BRCAm HRRm • All • Non HRRm 	
To assess the efficacy of the combination of ceralasertib +olaparib and the combination of AZD1775+olaparib compared with olaparib monotherapy in terms of OS
	
Time to death for any cause

 • BRCAm • HRRm • Non BRCAm HRRm • All • Non HRRm 	
To compare the efficacy of the combination of ceralasertib +olaparib with the combination of AZD1775+olaparib in terms of
 
 • PFS • ORR 	
PFS and objective response using BICR according to RECIST 1.1 Sensitivity analysis of PFS and objective response using Investigator assessments according to RECIST 1.1


 • BRCAm • Non BRCAm HRRm • Non HRRm 	
To compare the efficacy of the combination of ceralasertib +olaparib with the combination of AZD1775+olaparib in terms of
 
 • DoR • tumour change 	
DoR and tumour change using BICR according to RECIST 1.1 Sensitivity analysis of DoR and tumour change using Investigator assessments according to RECIST 1.1

 • BRCAm • HRRm • Non BRCAm HRRm • All • Non HRRm 	
To compare the efficacy of the combination of ceralasertib +olaparib with the combination of AZD1775+olaparib in terms of OS
	
Time to death for any cause

Patient Population	Secondary Objectives	Outcome Measures

 All 	To explore the frequency of and describe the nature of tumour HRR (including BRCA) mutation(s) in tumour samples and to compare this with germline HRR (including BRCA) mutation status	Tumour and germline mutation status of CC1 genes

 All 	To assess exposure to olaparib, ceralasertib and AZD1775 in all patients	$C_{\min ss}$

For patient populations based on single tumour gene-based strata, unweighted analyses will be conducted; for patient populations based on a combination of tumour gene-based strata, weighted analyses (with weights derived as described in Section 8.5.1) will be conducted.

8.5.2.1 Analysis of objective response

Objective response will be analysed using logistic regressions with a covariates study treatment and prior platinum-based therapy. The results of the analysis will be presented in terms of an odds ratio for study treatments together with associated 90% profile likelihood CI and 2-sided p-values. P-values will be based on twice the change in log-likelihood resulting from the addition of covariate study treatment to the model containing only the covariate related to prior platinum-based therapy.

8.5.2.2 Analysis of DoR

In order to analyse the secondary outcome variable, DoR between treatment arms, the Expected Duration of Response (EDoR) will be derived for each treatment arm. The EDoR is the product of the proportion of patients responding to treatment and the mean DoR in responding patients, and provides an estimate based on all randomised patients.

Study treatments will be compared (stratified for prior platinum-based therapy) by calculating pair-wise ratios of EDoRs (including 90% CIs) using an appropriate probability distribution for DoR in responding patients. The choice of probability distribution will be detailed in the SAP.

Additionally, descriptive data will be provided for the DoR in responding patients, including associated KM curves.

8.5.2.3 Analysis of Tumour Size Change at Week 16

The absolute change in TL tumour size from baseline and percentage change in TL tumour size from baseline will be summarized using descriptive statistics by study treatment.

The effect of study treatments on absolute and percentage change in TLs tumour size at Week 16 will be estimated from an analysis of covariance model including a term for the absolute (percentage) change in Week 16 value, a covariate for baseline TLs tumour size, a covariate for prior platinum-based therapy and a covariate for the time from the baseline scan to randomisation. The number of patients, unadjusted mean and least-squares means for each treatment arm will be presented, together with the difference in least-squares means, 90% Cis and corresponding 2-sided p-values.

8.5.2.4 Analysis of OS

OS data will be analysed using the same methodology and model as for the analysis of PFS described in Section 8.5.1 (provided there are sufficient events available for a meaningful analysis, if not, only descriptive summaries will be provided).

8.5.2.5 CCI

The statistical analysis of the CCI variables will be described in the SAP.

8.5.2.6 Pharmacokinetics

Plasma concentrations for each of the drug substances measured within each of the treatment arms together with any associated metabolites will be listed by nominal sample time. In addition, minimum concentrations at steady state ($C_{\min ss}$) will be summarised using appropriate summary statistics. Further details will be provided in the SAP.

The plasma concentration data for olaparib, AZD1775 and/or ceralasertib will be analysed using a population PK approach, which may include exploring the influence of covariates on PK where appropriate and may be combined with other studies' data. In addition, a population PDx approach will be used to investigate the relationship between PK and selected primary, secondary, and/or exploratory endpoints, where deemed appropriate.

The data analysis plan and results of such population PK and PKPDx analyses will be reported separately from the CSR.

8.5.3 Safety and tolerability variables

- Safety and tolerability variables will be summarized descriptively by treatment arm for the Safety Analysis Set:
- AEs, laboratory test results, categorical ECG data and ECOG PS will be summarized by incidence estimates, overall and by CTCAE grading (laboratory tests in addition also by shift tables), where applicable.

Time course of laboratory test results, vital signs and continuous ECG data will be summarized graphically.

8.5.4 Subgroup analysis (if applicable)

Any additional subgroup analyses will be described in the SAP.

8.5.5 Interim analyses

For the non HRR m population an interim analysis will be triggered when 75 patients have been recruited and assessed for at least 8 weeks, in order to assess the proportion of patients with NPD based on the Investigator assessment at 8 weeks in each of the treatment arms. With approximately 25 patients in each treatment arm, if the 80% two-sided upper CI for the proportion of patients with NPD is less than 56% (O'Shaughnessy et al 2014) and with consideration of this analysis in context with the totality of the clinical data (safety and efficacy) available, the URC may recommend to cease recruitment in this arm and no further patients will be recruited into that treatment arm in the non HRR m population. Recruitment will be paused after the 75th patient has been recruited into the population, until the AZ URC confirms the strata and which treatment arms should be reopened.

A further NPD futility interim analysis, using the same criteria, in the non *BRCAm* HRR m population may be performed, if the outcome of the interim analysis in the non HRR m population resulted in treatment arms being stopped.

As the “non HRR m ” patient population is expected to be enrolled quicker than the other patient populations, the first PFS interim analysis for patient population “non HRR m ” is triggered when 44 PFS events for the ceralasertib +olaparib vs. olaparib monotherapy pairwise comparison (65% of planned number of PFS events) have occurred in stratum C.

The second PFS interim analysis for patient populations “*BRCAm*” and “non *BRCAm* HRR m ” is triggered when 44 PFS events for the ceralasertib +olaparib vs. olaparib monotherapy pairwise comparison (65% of planned number of PFS events) have occurred in each of the two strata A and B.

The PFS interim analyses may be concurrent or separate depending on the PFS event rates in the three strata and operational requirements, so if the timings for the *BRCAm* and non *BRCAm* HRR m populations are not concurrent, separate interims may be needed for each patient population. The purpose of the interim analyses is to provide the opportunity (details will be specified in the URC Charter) for an early trigger to commence a phase III study, if the results are strong enough.

An initial OS analysis will be performed at the same time as the primary analysis of PFS and will use the same methodology and model. A further analysis of OS will be performed when the OS data are approximately 70% mature; this is anticipated to occur approximately 42 months after first patient in.

8.5.6 Exploratory analysis

The statistical analysis of exploratory outcome variables will be described in the SAP.

9. STUDY AND DATA MANAGEMENT BY ASTRAZENECA

9.1 Training of study site staff

Before the first patient is entered into the study, an AstraZeneca representative will review and discuss the requirements of the Clinical Study Protocol and related documents with the investigational staff and also train them in any study specific procedures, CCI CCI s and the Clinical Database utilised as well as on the handling of samples for both the local and the central laboratory.

The PI will ensure that appropriate training relevant to the study is given to all of these staff, and that any new information relevant to the performance of this study is forwarded to the staff involved.

The PI will maintain a record of all individuals involved in the study (medical, nursing and other staff).

9.2 Monitoring of the study

During the study, an AstraZeneca representative will have regular contacts with the study site, including visits to:

- Provide information and support to the Investigator(s).
- Confirm that facilities remain acceptable.
- Confirm that the investigational team is adhering to the Clinical Study Protocol, that data are being accurately and timely recorded in the CRFs, that biological samples are handled in accordance with the Laboratory Manual and that study drug accountability checks are being performed.
- Perform source data verification (a comparison of the data in the CRFs with the patient's medical records at the hospital or practice, and other records relevant to the study) including verification of informed consent of participating patients. This will require direct access to all original records for each patient (eg, clinic charts).
- Ensure withdrawal of informed consent to the use of the patient's biological samples is reported and biological samples are identified and disposed of/destroyed accordingly, and the action is documented, and reported to the patient.

The AstraZeneca representative will be available between visits if the Investigator(s) or other staff at the centre needs information and advice about the study conduct.

9.2.1 Source data

The investigator must maintain accurate documentation (source data) that supports the information entered in the eCRF.

Source documents provide evidence for the existence of the subject and substantiate the integrity of the data collected. Source documents are filed at the investigator's site.

Data reported on the eCRF that are transcribed from source documents must be consistent with the source documents, or the discrepancies must be explained. The investigator may need to request previous medical records or transfer records, depending on the study. Also, current medical records must be available.

Source data includes all information in original records and certified copies of original records or clinical findings, observations, or other activities in a clinical trial necessary for the reconstruction and evaluation of the trial.

Refer to the CSA for location of source data.

9.2.2 Study agreements

The PI at each/the centre should comply with all the terms, conditions, and obligations of the CSA, or equivalent, for this study. In the event of any inconsistency between this Clinical Study Protocol and the CSA, the terms of Clinical Study Protocol shall prevail with respect to the conduct of the study and the treatment of patients and in all other respects, not relating to study conduct or treatment of patients, the terms of the CSA shall prevail.

Agreements between AstraZeneca and the PI should be in place before any study-related procedures can take place, or patients are enrolled.

9.2.3 Archiving of study documents

The Investigator follows the principles outlined in the CSA.

9.3 Study timetable and end of study

Final analysis for PFS per stratum

The data cut off (DCO) for the final analysis for PFS for each of the 3 strata (non HRR*m*, BRCA*m* and non BRCA*m* HRR*m*) will occur when at least 68 PFS events for the ceralasertib +olaparib vs. olaparib monotherapy pairwise comparison in that particular population has occurred.

The database will close to new data entry for patients at the time of the DCO of the final analysis for PFS analysis in each stratum (non HRR*m*, BRCA*m* and non BRCA*m* HRR*m*) is met with the exceptions described below:

Patients on treatment

Patients who are receiving study treatment at the time of the data cut-off can either choose to discontinue from the study or, when the investigator believes patients are gaining clinic benefit, patients may continue to receive study treatment within the study. It is recommended

that the patients continue the scheduled protocol visits and Investigators monitor the patient's safety laboratory results prior to and periodically during treatment with study treatment in order to manage AEs in accordance with the Dose Modification and Toxicity Management Guidelines (see Section 6.8). Data will no longer be required to be entered into the clinical database for the stratum that has met the trigger for the final analysis for PFS with the exception of the following data which must continue to be recorded in the eCRF (Table 6):

1. IP dispensation and accountability
2. Laboratory Safety Assessments
3. Pregnancy Test (In the event of a pregnancy within the reporting timelines outlined in section 6.6 the PREGREP module in the CRF will be completed to report the pregnancy and the PREGOUT will be used to report the outcome of the pregnancy.
4. AEs and SAEs

The required blood sample for CCI at the time of progression should be collected. Wherever possible the optional tumour biopsy should be collected at the time of progression and processed as per the study laboratory manual.

If a patient subsequently discontinues treatment then the 30 days follow up visit should be completed and laboratory safety assessments, pregnancy test and adverse events should be recorded in the eCRF. The patients should then be followed for survival and anti-cancer therapy collected (see Table 4 and Table 5), data should be recorded in the patient notes and captured in the eCRF and reported for the purposes of this study until the Final OS analysis.

Patients in Survival Follow Up

For patients who have discontinued treatment and are in survival follow up at the time of the data cut off for the final analysis for PFS, survival and subsequent cancer therapy data will continue to be collected in the eCRF and reported for the purposes of the study until the final OS Analysis.

All SAEs that occur in patients still receiving study treatment (or within the 30 days following the last dose of study treatment) post the final DCO and database closure must be reported as detailed in Section 6.3.1.

Final OS Analysis

The end of the study is defined as the point that the final OS analysis is completed for all three strata.

Following the data cut off for the final OS Analysis, the clinical study database will close to new data. Patients are, however, permitted to continue to receive study treatment beyond the closure of the database if, in the opinion of the Investigator, they are continuing to receive benefit from treatment with study treatment. For patients who do continue to receive treatment beyond the time of this data cut-off, Investigators will continue to report all SAEs to

AstraZeneca Patient Safety until 30 days after study treatment is discontinued, in accordance with Section 6.4 (Reporting of SAEs). If an Investigator learns of any SAEs, including death, at any time after a patient has completed the study, and he/she considers there is a reasonable possibility that the event is causally related to the IP, the Investigator should notify AstraZeneca, Patient Safety. Additionally, as stated in Section 6.3 (Recording of AEs), any SAE or non serious AE that is ongoing at the time of this data cut-off, must be followed up to resolution unless the event is considered by the Investigator to be unlikely to resolve, or the patient is lost to follow-up.

A Clinical Study Report will be prepared.

The study started in Q1 2018 and to end by approximately Q4 2020.

The study may be terminated at individual centres if the study procedures are not being performed according to Good Clinical Practice (GCP), or if recruitment is slow. AstraZeneca may also terminate the entire study prematurely if concerns for safety arise within this study or in any other study with olaparib.

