3.8.1 Procedures for discontinuation of a patient from IP

At any time, patients are free to discontinue IP or withdraw from the study (ie, IP and assessments – see Section 3.9), without prejudice to further treatment. A patient that decides to discontinue IP will always be asked about the reason(s) and the presence of any AEs. If possible, they will be seen and assessed by an Investigator(s). Adverse events will be followed up (See Section 6); CCI (eg, for CCI) and all study drugs should be returned by the patient.

By discontinuing from study treatment, the patient is not withdrawing from the study. Patients should be followed for progression (if discontinuation in the absence of progression) and OS following treatment discontinuation as per the protocol schedule.

A patient can discontinue one of the combination drugs for up to 28 days. However, if they need to discontinue one of the combination drugs permanently, they will have to discontinue both combination drugs permanently. Following the ISRC meeting on 17 April 2019 a recommendation was made to close the AZD1775+olaparib treatment arm across all biomarker strata and that patients currently receiving treatment with AZD1775+olaparib treatment be offered the opportunity to continue treatment of olaparib monotherapy at the approved dose (300 mg bd). Any patient discontinuing IP should be seen at 30 days post discontinuation for the evaluations outlined in the study schedule. The patient's tumour status should be assessed clinically and, if appropriate, disease progression should be confirmed by radiological assessment. After discontinuation of study medication, the Principal Investigator (PI)/Sub-Investigator will perform the best possible observation(s), test(s) and evaluation(s) as well as give appropriate medication and all possible measures for the safety of the patient. In addition, they will record on the electronic Case Report Form (eCRF) the date of discontinuation, the reasons, manifestation and treatment at the time of discontinuation. If patients discontinue study treatment, the Study Monitor must be informed immediately. Patients will be required to attend the treatment discontinuation visit. The patient should return all study medication.

Any AEs that are unresolved at the patient's last AE assessment in the study are followed up by the Investigator for as long as medically indicated, but without further recording in the

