CRF. AstraZeneca retains the right to request additional information for any patient with ongoing AE(s)/SAE(s) at the end of the study, if judged necessary. Patients should be seen at least 30 days after discontinuing study medication to collect and/or complete AE information. For guidance on reporting AEs after the 30-day follow up period see Section 6.3.1.1.

Any patient who has not yet shown objective radiological disease progression at withdrawal from IP should continue to be followed as per RECIST 1.1.

All patients must be followed for survival, up to the final OS analysis (i.e. when OS data for the ceralasertib+olaparib vs. olaparib monotherapy pairwise comparison is approximately 70% mature).

If a patient is withdrawn from study, see Section 3.9.

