3.9.2 Withdrawal of the informed consent

Patients are free to withdraw from the study at any time (IP and assessments), without prejudice to further treatment.

A patient who withdraws consent will always be asked about the reason(s) and the presence of any AEs. The Investigator will follow up AEs outside of the clinical study.

If a patient withdraws from participation in the study, then his/her enrolment/randomisation code cannot be reused. Withdrawn patients will not be replaced.

If a patient withdraws consent, they will be specifically asked if they are withdrawing consent to:

- further participation in the study including any further follow up (eg, survival calls)
- withdrawal of consent to the use of their study generated data
- withdrawal to the use of any samples (see Section 5.7.4)

The status of ongoing, withdrawn (from the study) and “lost to follow-up” patients at the time of an OS analysis should be obtained by the site personnel by checking the patient notes, hospital records, contacting the patient’s general practitioner and checking publicly available death registries. In the event that the patient has actively withdrawn consent to the processing of their personal data, the vital status of the patient can be obtained by site personnel from publicly available resources where it is possible to do so under applicable local laws.

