3.4.4 Overall survival

Overall survival (time to death for any cause) is defined as the time from the date of randomisation until death due to any cause regardless of whether the patient withdraws from randomised therapy or receives another anti-cancer therapy (i.e. date of death or censoring – date of randomisation + 1). Any patient not known to have died at the time of analysis will be censored based on the last recorded date on which the patient was known to be alive.

For each OS analysis, survival calls will be made within 2 weeks following the respective data cut-off (DCO) date, and if a patient is confirmed to be alive, or if the patient’s death date is post the DCO date, these patients will be censored at the DCO date.

The status of patients completely withdrawn from the study or “lost to follow-up” at the time of each OS analysis should be obtained by the site personnel by checking the patient’s notes, hospital records, contacting the patient’s general practitioner and checking publicly-available death registries. In the event that the patient has actively withdrawn consent to the processing of their personal data, the vital status of the patient can be obtained by site personnel from publicly available resources where it is possible to do so under applicable local laws.

3.4.5 [Redacted]

In this study, [Redacted] will be assessed using the [Redacted]

[Redacted] will be given to the patients during screening, on Day 1 of Cycle 1 (baseline prior to first dosing of study treatment) and every 8 weeks thereafter until discontinuation of study treatment. Patients are to [Redacted] during their clinic visit. The site staff will enter the information directly into the Clinical Database.

[Redacted]

[Redacted]

[Redacted]

[Redacted]

[Redacted]

[Redacted]

[Redacted]

[Redacted]

[Redacted]

CCI [REDACTED]

- CCI [REDACTED]
- CCI [REDACTED]
- CCI [REDACTED]
- CCI [REDACTED]

CCI [REDACTED]

CCI [REDACTED]

CCI [REDACTED]

- CCI [REDACTED]
- CCI [REDACTED]

CCI [REDACTED]

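### Protocol 9.3 lets patients on treatment at the final PFS cut-off leave the study, which contradicts 3.8.1 and can cut short survival follow-up before the final OS analysis

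*Protocol*

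**What the plan says.** Protocol 9.3 closes the database for a stratum at its final PFS cut-off, with listed exceptions. For patients on treatment it states: "Patients who are receiving study treatment at the time of the data cut-off can either choose to discontinue from the study". The alternative is to go on receiving treatment within the study if the investigator sees benefit.

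Section 9.3 then describes survival collection after the cut-off for two groups:
- Patients who continue and later stop treatment have a 30-day visit, after which: "The patients should then be followed for survival and anti-cancer therapy collected".
- The second group is introduced with "For patients who have discontinued treatment and are in survival follow up at the time of the data cut off for the final analysis" of PFS.

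Protocol 3.8.1 gives the general rule: "By discontinuing from study treatment, the patient is not withdrawing from the study", and "All patients must be followed for survival, up to the final OS analysis".

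Protocol 3.9 lists voluntary withdrawal as a reason for leaving the study. Under 3.9.2 a patient who withdraws consent is asked specifically whether this covers "further participation in the study including any further follow up (eg, survival calls" and similar contacts). The same section says that the status of ongoing, withdrawn and lost-to-follow-up "patients at the time of an OS analysis should be obtained by the site personnel by checking the patient notes, hospital records", the general practitioner and death registries. SAP 3.4.4 repeats this for withdrawn and lost patients, whose status "at the time of each OS analysis should be obtained by the site personnel".

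Protocol Table 6 governs eCRF entry for patients on treatment after the cut-off. It has columns for treatment discontinuation, the 30-day visit and 8-weekly survival follow-up, and rows for survival and anti-cancer therapies.

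**The concern.** Section 9.3 sets leaving the study against continuing treatment within it. It does not name the option that 3.8.1 treats as normal, which is to stop treatment and stay in follow-up. A site that follows 9.3 may record a study exit; a site that follows 3.8.1 will keep contacting the patient. Nothing says which section governs.

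OS is a secondary endpoint in all five populations. Subsequent therapies are also to be taken into account when OS is assessed (Protocol 7.7), and the prompt for late MDS/AML and new malignancies runs through OS follow-up (Protocol 6.3.1.1). OS is censored at the date last known alive. The patients offered exit are largely those still free of a PFS event. If the combination prolongs PFS, more of them are in that arm, so any censoring from exits would be related to both outcome and arm.

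**Working it through.** **1. The plan's own figure.** Protocol 8.2 gives 68 events for 80% power, two-sided 10% level, HR 0.55, with 1:1 allocation for the sized comparison. The Schoenfeld formula is d = 4(z₀.₉₅ + z₀.₈₀)² / (ln HR)².
- HR 0.55: 4 × (1.645 + 0.842)² / 0.5978² = 69.2, with power 79.4% at 68 events.
- HR 6/11 = 0.545, from the stated medians of 6 and 11 months: 67.3, rounded up to 68, with power 80.4%.

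The 68 is reproduced.

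**2. Patients still event-free at the cut-off.** With about 50 per arm, 100 − 68 = 32 patients in the sized comparison are event-free when the cut-off is triggered. This holds whatever the treatment effect.

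**3. Split by arm.** Assume exponential PFS (as in Protocol 8.2) and uniform accrual over R = 15 months. The plan says recruitment is non-linear, so uniform is my assumption. The event-free proportion at calendar time T is e^(−λT)(e^(λR) − 1)/(λR), with λ = ln 2 / median.
- Olaparib, median 5 months: λ = 0.1386. Combination at HR 0.55: λ = 0.0762.
- T giving 68 expected events: about 19.6 months.
- Olaparib: 50 × 0.221 = 11.1. Combination: 50 × 0.419 = 20.9.

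| Olaparib median | HR | Accrual | Cut-off (months) | Event-free, olaparib | Event-free, combination |
|---|---|---|---|---|---|
| 5 | 0.55 | uniform | 19.6 | 11.1 | 20.9 |
| 5 | 0.55 | back-loaded | 21.8 | 10.9 | 21.1 |
| 6 | 0.55 | uniform | 21.7 | 10.9 | 21.1 |
| 6 | 0.55 | back-loaded | 23.9 | 10.8 | 21.2 |
| 5 or 6 | 1.0 | either | 17.0–20.5 | 16.0 | 16.0 |

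Back-loaded means that the cumulative share recruited by month t is (t/15)².

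**4. Follow-up exposed.** The final PFS analysis is expected at about 24 months (Protocol 8.2) and the final OS analysis at about 42 months (Protocol 8.5.5): 42 − 24 = 18 months.

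**5. Possible effect on OS (illustration only).** A simulation of 3,000 trials per scenario used an olaparib median PFS of 5 months, HR 0.55 and uniform accrual. It also assumed exponential survival after progression with a 9-month median in both arms, which the documents do not give. All event-free patients were taken to be on treatment. The final OS date was the 70th death under complete follow-up.

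| Share of event-free patients who leave | Vital status later retrieved | Deaths observed | OS HR |
|---|---|---|---|
| none | – | 70 | 0.68 |
| 25% | none | 67 | 0.69 |
| 50% | none | 63 | 0.70 |
| all | none | 57 | 0.77 |
| all | 80% | 67 | 0.69 |

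The shift is towards no effect. It is small unless nearly all leave and nothing is retrieved.

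**The case against.** The strongest reply is that no sentence in 9.3 says survival follow-up stops. The rule in 3.8.1 covers all patients. A patient who stops at the cut-off can be read as one who later discontinues treatment, and so is covered by 9.3 itself. Table 6 already provides the 30-day and survival entries. Voluntary withdrawal is a listed reason under 3.9. Survival calls follow every OS data cut-off (Protocol 8.4.1, SAP 3.4.4), and the first OS analysis coincides with the final PFS analysis. Sites must seek the vital status of withdrawn patients, and SAP 4.2.8.6 reports premature OS censoring by arm.

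Most of this stands. It rules out three stronger readings that a reader might infer:
- *That exit ends survival follow-up and no survival data are entered.* The documents require follow-up or retrieval in several places. The risk is incomplete data.
- *That a known share leaves, so that the 70% OS maturity trigger must be met from fewer patients.* The documents give no uptake rate, and benefiting patients may stay on treatment. The inference also needs retrieval to fail completely.
- *That the better arm necessarily loses more, and loses its longest-controlled patients.* The imbalance needs a PFS effect. The pool also includes recently randomised patients.

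The reply does not remove the contradiction. Table 6 is written for patients on study treatment after the cut-off, so it does not clearly cover someone who leaves at that point. The required search is for survival status; it does not replace 8-weekly contact or collection of subsequent therapy. It depends on available records and, where consent to data processing is withdrawn, on local law. The SAP summaries would describe the censoring but not prevent it.

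**Conclusion.** The point holds as a contradiction between Protocol 9.3 and 3.8.1. Followed literally, 9.3 can cause avoidable loss of survival and subsequent-therapy data over about 18 months.

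The pool is roughly 32 of 100 patients per stratum at most. The split of about 11 to 21 rests on 50 per arm, exponential PFS and the design HR, and becomes even if there is no PFS effect. The ceiling is approximate: some event-free patients will already have stopped treatment, and Protocol 3.8 allows treatment beyond progression. The number who would leave cannot be derived from the documents.

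The primary PFS analysis is unaffected, because the option arises only at the final PFS cut-off. OS is a secondary endpoint for which the study is not sized. Severity is minor to moderate.

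**What to change.** In Protocol 9.3, replace the option to leave the study with an option to discontinue study treatment. State that such patients have the 30-day visit and are then followed for survival and subsequent anti-cancer therapy to the final OS analysis, recorded in the eCRF as in Table 6. The exception is a patient who specifically withdraws consent to follow-up under 3.9.2. Cross-reference 3.8.1, and make clear that Table 6 covers patients who stop at the cut-off itself.

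The change concerns follow-up and data entry only; who may stop or continue treatment is unchanged. It costs a short protocol correction and a letter to sites. The 8-weekly survival contacts are already required by 3.8.1, and the SAP needs no change.
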